Official Study Title: Role of Endoscopic Ultrasound Guided Fine Needle Aspiration of Portal Vein Thrombus in the Diagnosis and Staging of Hepatocellular Carcinoma.

Document Title: Study Protocol.

Document Date: 7th March 2019

Introduction

Portal vein thrombosis (PVT) is being increasingly diagnosed. It has a wide ranging clinical spectrum from being an asymptomatic state to a potentially life-threatening situation. It is not unusual to find it as an incidental finding in the abdominal imaging done for other reasons. It is commonly associated with cirrhosis and abdominal malignancies and also has a strong association with prothrombotic disorders.

A neoplastic thrombus of the portal vein is found in 6.5%–44% of patients with hepatocellular carcinoma (HCC). Bland (Non-malignant) thrombus occurs in patients with and those without malignant disease. Bland thrombus occurs in 4.5%–26% of patients with chronic liver disease and in 42% of patients with HCC. In addition, bland and tumor thrombi can be coexistent.

Presence of neoplastic thrombus serves as an important determinant of tumor staging, as well as prognosis, and influences treatment selection. In some cases, it may be even the initial sign of an undetected HCC. Therefore, the detection of portal vein thrombus and accurate differentiation of bland from neoplastic thrombus are crucial for patient treatment.

Portal vein tumor thrombosis (PVTT) on imaging studies appears as a low-density plug within a dilated main or lobar portal vein. This plug enhances with contrast in the arterial phase on both CT and MRI and may have arterial signal on Doppler US. Non tumor portal vein thrombosis has a similar appearance to PVTT; however, it does not enhance with contrast nor does it have any Doppler signal. Therefore, whenever a PVT enhances with contrast or has a Doppler signal, PVTT remains the diagnosis until proved otherwise.

Since not every PVT in a patient with HCC is a tumor thrombus, since the nature of the thrombus will ultimately determine the course of treatment, and since PVT may be even the initial sign of an undetected HCC, every effort should be made to distinguish between a tumor and a non-tumor PVT. In addition, malignant PVT does not always demonstrate neovascularity and/or enhancement, which makes FNA necessary in order to characterize the nature of the PVT.

Sampling of portal vein thrombus with trans-abdominal ultrasound guidance may lead to erroneous results because of inadvertent inclusion of normal hepatocytes or associated liver masses. Further, potential adverse events of trans-abdominal PV sampling include serious biliary and/or vascular injury.

In contrast to the percutaneous approach, EUS provides a unique view and access to the main portal vein. From the duodenal bulb and second part of the duodenum, the portal vein can be visualized from the confluence of the splenic and superior mesenteric veins into the porta hepatis. Periportal collateral vessels or cavernous transformation of the portal vein, which commonly are associated with portal vein thrombosis, are also easily and reliably detected by EUS instruments with color Doppler US capability approach.

With a linear-array echo-endoscope, the portal vein can be punctured easily with a fine needle under direct visualization, while avoiding the adjacent hepatic artery, bile duct, and collateral vessels (if present). Because the approach is not trans-hepatic, it eliminates any need to avoid the primary tumor and any possibility of contaminating the specimen with hepatocytes, as can occur if the needle tracks through the liver parenchyma. Thus, the rate of false-positive diagnoses is likely to be lower with the EUS compared with the percutaneous approach.

Multiple case reports and case series have demonstrated the safety and efficacy of FNA of PVT. The vast majority of the published literature describes percutaneous US-guided FNA of a PVT, with only few reports noting the use of EUS-guided FNA.

Aim of Work

- 1) To assess the usefulness of using EUS-FNA in determining the percentage error in triphasic abdominal CT in the diagnosis of malignant portal vein thrombus.
- 2) To assess the ease and safety of EUS-FNA as an invasive maneuver.

Patients:

Study Design:

This is a pilot study that will include 30 patients with liver cirrhosis and portal vein thrombus which don't fulfill the criteria of malignancy by imaging technique. The patients will be involved in the study will be admitted to Specialized Medical Hospital, Mansoura University Hospitals.

Inclusion Criteria:

- Patients with liver cirrhosis and PVT which don't fulfill criteria of malignancy by triphasic CT abdomen defined as, (neovascularity of thrombus, arterial enhancement with rapid washout, direct invasion by adjacent hepatic mass and diameter of thrombus more than 23 mm), either :
 - With or without hepatic mass

- Undergone local treatment or surgical treatment following a diagnosis of HCC and develop PVT during their follow up.

Exclusion criteria:

- Uncooperative or excessively apprehensive patient
- Anticoagulation treatment or non-substituted coagulopathy (International Normalized Ratio ≥ 1.5 , Platelet count ≤ 50.000 cells/mm³, heparin administration at therapeutic doses).
 - Inhibition of platelet aggregation by clopidogrel and other thienopyridines.
 - Contraindications of sedation (Uncontrolled Diabetes Mellitus, Uncontrolled Thyroid Disorders, Pregnancy, Respiratory Embarrassment, Reactional Drugs like Antidepressants and Anti-anxiety Agents).
 - Patients fulfilling criteria of malignancy by triphasic CT on abdomen.
 - Extra hepatic metastasis of HCC.
 - Child-Pugh classification stage C.

Study end-points:

- 24 months from the start of the research.

Methods:

Patients will be included in this study will be subjected to the following:

- I.** The study will be explained to all participants in the study, and an informed written consent will be obtained from them before starting the study.

II. Medical history:

Detailed history was taken with stress on:

- Signs of cachexia (unintentional weight loss, progressive muscle wasting, and a loss of appetite)
 - Low grade fever
 - Recent onset fatigue
 - Abdominal pain
 - Dyspepsia
 - Hematemesis and melena
 - Back ache

III. Full clinical examination with special stress on:

- Vital signs including: pulse, arterial blood pressure, temperature, respiratory rate.
- Abdominal Lumps and/or tenderness

IV. Laboratory investigations:

Complete blood count, International Normalized Ratio, Liver enzymes, Serum albumin, Serum bilirubin and Serum creatinine.

V. Radiology: Abdominal ultrasound for initial assessment, Abdominal CT (Contrast Enhanced) (Number of HCC nodules if present, diameter of largest HCC nodule in centimeters, nature of PVT, presence of abdominal metastases if present), Non contrast CT chest to exclude pulmonary metastasis, Bone survey to exclude bone infiltrates.

VI. EUS-FNA:

EUS-FNA will be performed in standard fashion. Under EUS guidance, the main, left and right portal veins will be identified. After verifying

flow signal by Doppler, a 25-gauge EUS-FNA needle will be advanced from the duodenal bulb or second part of the duodenum into the portal vein, 1-2 passes through portal vein thrombus will be taken to ensure adequate cellularity for histopathology. The puncture site will be monitored under EUS for complications.

Study outcomes:

Histopathology of biopsies taken from bland portal vein thrombus which diagnosed by triphasic CT abdomen to evaluate the possibility of malignant PVT that was not discovered by imaging technique (Abdominal ultrasound and triphasic abdominal CT).

Sample size:

One of the goals of a pilot study is to identify unforeseen problems.

Malignant PVT may be an unforeseen problem in patients with liver cirrhosis and / or HCC if not detected by imaging modalities.

This small-scale pilot study will examine the practicality and feasibility of EUS in diagnosing malignant PVT not detected by imaging studies.

With a prevalence of 10%, malignant PVT not detected by imaging studies will almost certainly be identified by EUS (with 95% confidence) in a pilot study including 30 participants.

This sample size was calculated by the following formula¹:

$$n = \frac{\ln(1 - \gamma)}{\ln(1 - \pi)}$$

Where,

n = Sample size of the pilot study.

\ln = Natural logarithm.

γ = Confidence level (chosen as 0.95)

π = probability (chosen as 0.10)

The result was 28.4 rounded to 29 participants.

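### Aim 1 measures CT error against unverified EUS-FNA alone, so the result is an FNA yield that tends to understate CT's misses if FNA false positives are rare

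*Protocol*

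**What the plan says.** Aim of Work, item 1, concerns the usefulness of EUS-FNA in "determining the percentage error in triphasic abdominal CT in the diagnosis of malignant portal vein thrombus". Under Study Design, the 30 participants have cirrhosis and a "portal vein thrombus which don't fulfill the criteria of malignancy by imaging technique". Patients who meet the CT malignancy criteria are excluded.

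The section Study outcomes gives one outcome: "Histopathology of biopsies taken from bland portal vein thrombus which diagnosed by triphasic CT abdomen to evaluate the possibility of malignant PVT". Methods VI describes a 25-gauge needle and says that "1-2 passes through portal vein thrombus will be taken to ensure adequate cellularity for histopathology". That section ends with observation of the puncture site for complications. It describes no repeat sampling, later imaging or clinical follow-up of a patient whose sample shows no malignant cells. The only time statement, under Study end-points, is "24 months from the start of the research", which limits the study and does not set follow-up for a patient.

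Two statements in the background bear on the accuracy of FNA. The Introduction says that "bland and tumor thrombi can be coexistent". On the EUS route, the protocol argues that "it eliminates any need to avoid the primary tumor and any possibility of contaminating the specimen with hepatocytes", and concludes that false positives are probably fewer than with percutaneous sampling. It gives no figure for FNA sensitivity or specificity.

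The section Sample size assumes that 10% of these patients have malignant thrombus missed by imaging, and claims with 95% confidence that EUS would identify it in 30 participants.

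**The concern.** Because every participant is CT-negative, the only CT error that this study can observe is a malignant thrombus called bland. FNA histopathology is the only reference. A malignant thrombus that the needle misses cannot enter the numerator but stays among the 30 in the denominator, so in the arithmetic it sits with the thrombi that CT classified correctly.

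The Introduction says that the nature of the thrombus decides treatment. If a low or zero count were reported as CT's percentage error, it could be read as reassurance about CT, when part of it may reflect the limits of the needle sample. The sample-size statement has the same gap: its formula has no term for FNA sensitivity and so treats every malignant thrombus as detected.

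**Working it through.** **Inputs from the protocol (Sample size):** probability π = 0.10, confidence γ = 0.95, 30 participants planned.

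**Assumed, because the protocol gives no figure:** FNA sensitivity Se from 0.60 to 0.90, and specificity Sp = 1 unless stated.

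**Step 1: the plan's own figure.** n = ln(1 − γ)/ln(1 − π) = ln(0.05)/ln(0.90) = 28.43, rounded up to 29. This reproduces the protocol. With 30 patients, P(at least one) = 1 − 0.90^30 = 0.958. The arithmetic is correct, with Se = 1 implied.

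**Step 2: expected observed proportion.** In general this is π·Se + (1 − π)(1 − Sp). With Sp = 1 it reduces to π·Se. In 30 patients, π implies 30 × 0.10 = 3 malignant thrombi, of which 3 × (1 − Se) are expected to be missed. P(at least one positive in 30) = 1 − (1 − 0.10·Se)^30. The n needed for 95% is ln(0.05)/ln(1 − 0.10·Se), rounded up.

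| Se | Expected observed proportion | Expected misses among 3 | P(at least one in 30) | n for 95% |
|---|---|---|---|---|
| 1.00 | 10% | 0 | 0.958 | 29 |
| 0.95 | 9.5% | 0.15 | 0.950 | 31 |
| 0.90 | 9% | 0.3 | 0.941 | 32 |
| 0.80 | 8% | 0.6 | 0.918 | 36 |
| 0.70 | 7% | 0.9 | 0.887 | 42 |
| 0.60 | 6% | 1.2 | 0.844 | 49 |

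At Se = 0.95 the unrounded probability is 0.9499, just short of 0.95, which is why the table gives n = 31 there. The 95% statement for 30 patients therefore needs a sensitivity of about 0.95 or higher.

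**Step 3: a zero count.** At a true 10%, P(no positive in 30) is 1 − 0.958 = 4.2% with perfect FNA, 1 − 0.941 = 5.9% at Se = 0.90 and 1 − 0.844 = 15.6% at Se = 0.60.

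**Step 4: when the direction would reverse.** False positives cancel the misses when (1 − π)(1 − Sp) = π(1 − Se), that is Sp = 1 − 0.10(1 − Se)/0.90. This gives Sp = 0.989 at Se = 0.90, 0.978 at 0.80, 0.967 at 0.70 and 0.956 at 0.60. Above these values the observed proportion understates the true one; below them it overstates it.

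**The case against.** The strongest reply is that this is a small pilot of feasibility. Its outcome is the detection of malignancy that imaging did not find, and showing that such cases exist does not require verified negatives. That stands for the detection purpose. It does not cover Aim 1, which names a percentage error of CT.

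A reader might infer that the protocol counts a negative FNA as a correct CT result. It does not say so, and it does not say how a low count will be reported. The point follows only from FNA being the sole reference. A reader might also infer that the estimate is biased downward whatever the circumstances, or that it is a guaranteed minimum. Neither is supported. The direction depends on few false positives. The protocol argues against hepatocyte contamination but gives no specificity, and by Step 4 a specificity of 0.956 to 0.989 would already cancel the misses. A proportion from 30 patients is also subject to sampling error and is no minimum for the population.

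The size of the shift is unknown, because 60% to 90% is an assumption. It is also smaller than the sampling error. An observed 3/30 has an exact 95% interval of about 2% to 27%, which contains the values corrected for sensitivity (10%/0.90 = 11.1% to 10%/0.60 = 16.7%). This limits the practical weight of the point. It does not remove it, since a larger sample would narrow the interval and leave the shift in place.

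Later imaging is only a partial check. The Introduction says that malignant thrombus does not always enhance or show neovascularity, so CT-silent tumor would stay hidden. Only the patients previously treated for HCC are described as being in follow-up, so later imaging may not exist for the others.

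**Conclusion.** The point holds in a limited form. As planned, the study estimates the proportion of CT-bland thrombi with malignant cells on EUS-FNA, which equals CT's error in these patients only if FNA is close to perfect. If false positives are rare, the result tends to understate that error by the factor Se: by 1 to 4 percentage points on a true 10% over the assumed 60% to 90%. The 95% detection statement is correct as arithmetic but holds only for a sensitivity of about 0.95 or more; over the assumed range the figure is 84.4% to 94.1%.

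The protocol itself fixes the reference standard, the wording of Aim 1 and the detection statement, so the point does not depend on what a statistical analysis plan might add. It is a low-cost improvement that changes what the trial can conclude. It does not invalidate the pilot.

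**What to change.** 1. In Aim of Work, item 1, and in Study outcomes, name the result *proportion of CT-bland thrombi with malignant cells on EUS-FNA (FNA yield)*. Add that it is likely to understate CT's error if FNA false positives are rare, and that a low or zero count is not to be read as showing that CT is accurate.
2. In Sample size, state that the 95% detection figure assumes FNA sensitivity near 1, and give the figure over a stated range of sensitivity, as in the table above.
3. Add a secondary outcome. At study close, review the records of FNA-negative patients for later malignant portal vein thrombus on whatever imaging or clinical evidence routine care has produced. Report the time since FNA, and list patients without later imaging as unverified.

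**Cost:** revised wording, a short table and one record review per FNA-negative patient, with no added procedure.

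**Limits:** a later malignant change may be new disease, CT-silent tumor will still be missed, and patients enrolled late will have little follow-up. The third item should therefore stay secondary. The first two do not depend on it.
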